### 5.4.2 Data on day of intubation OR admission to ICU if transferred from another hospital with mechanical ventilation

- Date of hospital admission;
- Date of ICU admission;
- Date and time of intubation (if possible, also in transferred patients);
- Transferred under ventilation (if applicable) (yes or no);
- Duration of ventilation in previous hospital (if applicable) (days);
- Use of non-invasive ventilation (NIV) before intubation (yes or no) and if so, duration (hours);
- Acute Physiology and Chronic Health (APACHE) II score or APACHE IV score, or Simplified Acute Physiology Score (SAPS) II;
- Sequential Organ Failure Scores (SOFA); and
- Plasma creatinine in 24 hours before admission/intubation (mmol/L)

### 5.4.3 Repeated measures

- Within one hour after initiation of ventilation OR within first hour of arrival when the patient has been intubated in another hospital, AND 3 times a day at fixed time points (8:00 AM, and 4:00 PM and 8:00 PM) for a following 3-day period:
  - Ventilation data
    - Ventilation mode;
    - Tidal volume set ( $V_T$ ) (mL);
    - Expiratory tidal volume (VTE);
    - Positive end-expiratory pressure (PEEP) (cm H2O);

- Maximum airway pressure ( $P_{\max}$ ) (cm H2O) or plateau pressure ( $P_{\text{plateau}}$ ) or peak pressure ( $P_{\text{peak}}$ ) (cm H2O);
  - Level of pressure support above PEEP (cm H2O);
  - Inspired fraction of oxygen ( $\text{FiO}_2$ ) (%);
  - Set measured respiratory rate (RR) (min);
  - Inspiration to expiration ratio (I:E) (ratio);
  - Saturation of peripheral oxygen ( $\text{SpO}_2$ ) (%); and
  - End-tidal carbondioxide ( $\text{ETCO}_2$ ) (kPa).
- Arterial blood gas (ABG) analysis
  - pH;
  - Partial pressure of oxygen ( $\text{PaO}_2$ ) (kPa or mmHg);
  - Partial pressure of carbon dioxide ( $\text{PaCO}_2$ ) (kPa or mm Hg);
  - Bicarbonate ( $\text{HCO}_3^-$ ) (mmol/L);
  - Arterial saturation of oxygen ( $\text{SaO}_2$ ) (%);
  - Arterial lactate levels (mmol/L);
  - $\text{FiO}_2$  (%) at time point of ABG; and
  - Position of patient in which ABG was taken.
- Hemodynamics
  - Mean arterial pressure (mmHg);
  - Heart rate (bpm);
- 3 times a day at fixed time points (8:00 AM, and 4:00 PM and 8:00 PM) for a following 3-day period:
  - Received paralytic drugs within the previous 8 hours (yes or no).
- Every day at 8:00 AM for 72-hour period after admission
  - Life status (alive or deceased);
  - Location (in ICU, hospital or other facility);
  - Intubation status;
  - Sequential Organ Failure Scores (SOFA);
  - Cumulative dose of sedatives (mg);
  - Cumulative dose of vasopressors (mg);
  - Cumulative fluid balance during last 24 hours (ml);
  - Amount of fluid administered during last 24 hours (ml);
  - Urine output (ml/hour); and

- Plasma creatinine (mmol/L).
- Prone position (yes or no), and if yes, time and duration (hours);
- ABG in supine position;
- Use of recruitment maneuver (yes or no);
- Undergoing veno–venous, veno–arterial or arterio–venous extracorporeal membrane oxygenation (ECMO) (yes or no);
- Pneumothorax (yes or no)

- Follow-up
  - Life status at day 7, day 28 and day 90;
  - Alive (yes or no), and if not, the date of passing;
  - Location (ICU, hospital, home);
  - Intubated (yes or no), and if not, extubation date;
  - Acute Kidney Injury (yes or no);
  - Date of discharge from ICU; and
  - Date of discharge from hospital.

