### **Methods**

In every patient, granular ventilator settings and parameters are collected from start of invasive ventilation for up to 72 hours. Patients will be followed up until ICU and hospital discharge, and until day 90.

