### **4.3 Exclusion criteria**

- Age <18 years
- Already included in the same study in another hospital
- Having had received invasive ventilation > 24 hours in a non–participating hospital

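### The baseline ventilation reading runs on two clocks (start of ventilation, or arrival after transfer), and the analysis plan does not separate or adjust for them when hospitals are compared

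*Combined protocol and SAP*

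**What the plan says.** The Summary (Methods) gives one time origin: settings and "parameters are collected from start of invasive ventilation for up to 72 hours". Section 5.4.3 gives two for the same first reading: "Within one hour after initiation of ventilation", or "within first hour of arrival when the patient has been intubated in another hospital". After that first reading, ventilation data are taken at three fixed clock times a day (8:00 AM, 4:00 PM, 8:00 PM) for three days.

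Two exclusions in Section 4.3 govern transfers: "Having had received invasive ventilation > 24 hours in a non–participating hospital" and "Already included in the same study in another hospital". The 24-hour limit applies only to ventilation in non-participating hospitals.

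Section 5.4.2 collects a yes/no field for transfer under ventilation, "Date and time of intubation (if possible, also in transferred patients") and "Duration of ventilation in previous hospital (if applicable) (days"). The same list records earlier non-invasive ventilation in hours.

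Section 7 specifies mixed models with hospital as a random effect. The prespecified subgroups are sex and body mass index. Neither transfer status nor time since intubation appears in it.

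**The concern.** The primary objective (Section 2.1.1) is to describe and compare settings across Dutch ICUs, and the hypothesis (Section 2.2.1 and the Summary) is that practice varies between them. A first-hour reading shows what a hospital sets when it starts ventilation. An arrival reading shows the settings of a patient who may be a day further into ventilation, possibly with settings chosen elsewhere, yet it is assigned to the receiving hospital. Hospitals that take many transfers could then differ at baseline from hospitals that intubate their own patients even if practice were identical. The artefact would point towards the variation that the study expects to find. The same ambiguity would carry into the association models if they use baseline settings as predictors.

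**Working it through.** The plan states no figure on this point, so there is none to reproduce. The check has three parts.

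**1. Time on the ventilator at the first reading**

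- Not transferred: 0 to 1 hour (Section 5.4.3).
- Transferred from a non-participating hospital: at most 24 h (Section 4.3) + T + 1 h (Section 5.4.3), where T is transport time. T is not given. For an assumed T of 0 to 4 h, the maximum is 25 to 29 h.
- Transferred from a participating hospital without having been included there: Section 4.3 sets no hour limit. Section 4.1 calls for consecutive patients, so most of these should already have been captured at the first hospital.

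**2. The later readings**

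The fixed times leave gaps of 8, 4 and 12 hours. In any patient, the first fixed reading can come anywhere from minutes to about 12 hours after the start of ventilation or arrival. Transfer adds the earlier ventilation and transport time to a series that was never aligned to intubation. The sharp contrast is therefore in the baseline reading, which is one of up to 1 + 3 × 3 = 10 readings.

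**3. Illustrative size**

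Let p be the share of transferred patients in a hospital, and d the mean change in a setting between a first-hour reading and an arrival reading. With identical practice:

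apparent difference between hospitals A and B = (pA − pB) × d

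The documents give neither p nor d. All values below are assumptions.

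| Setting | d | Share difference | Apparent difference |
|---|---|---|---|
| FiO2, full 24-h delay | 10 to 30 points | 0.10 to 0.30 | 10 × 0.10 = 1 to 30 × 0.30 = 9 points |
| FiO2, mid-range | 20 points | 0.20 | 20 × 0.20 = 4 points |
| A pressure | 1 to 3 cm H2O | 0.30 − 0.05 = 0.25 | 0.25 to 0.75 cm H2O |
| Any | any | 0 | 0 |
| Any | 0 | any | 0 |

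The FiO2 rows apply the whole first-day change to every transferred patient. If the mean delay were 12 h and the change linear, the range would halve, to 0.5 to 4.5 points.

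Across many hospitals, the artificial between-hospital SD is (SD of p) × d. For an SD of p of 0.05 to 0.20 and d of 1 to 3 cm H2O, that is 0.05 × 1 = 0.05 to 0.20 × 3 = 0.6 cm H2O.

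A random effect for hospital does not remove this. It accounts for clustering, but the artefact is part of the hospital effect. A patient-level term for transfer can separate it, because transfer status varies within hospitals.

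**The case against.** The strongest reply is that the arrival clock is a deliberate and disclosed choice in an urgent retrospective review, where the sending hospital's readings may be out of reach. The transfer field and, where obtainable, the intubation time are collected, so the issue can be handled in analysis without new data. This largely stands: the arrival clock itself is defensible. What is missing is any rule in Section 7 for handling it.

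The reply also disposes of several stronger readings:

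- A reader might infer that the plan states that the two kinds of reading are pooled. It does not. Section 5.4.3 lists them as one time point and Section 7 plans no separation, so pooling is the natural inference. Section 7 does not say which reading enters any model.
- A reader might infer that every later reading shifts by the same delay. The fixed clock times rule that out.
- A reader might infer that the arrival reading mainly shows the sending or transport team's settings. Nothing in the documents establishes this, and the receiving team may change settings within the hour. Inherited settings are a possibility only.
- A reader might infer that the 24-hour exclusion cannot be verified. It can be, wherever intubation time is recorded, and a field in days does not exclude decimals. The unit is nevertheless a poor match for an hour-based criterion.
- Starting transferred patients at the next fixed time point might look like a remedy. That point may fall minutes or 12 hours after arrival, so it neither clears inherited settings reliably nor aligns time since intubation.

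**Conclusion.** The point holds in a limited form. As written, the data rule puts readings at 0–1 hour and readings at up to about 25 hours plus transport into one baseline, and the plan has no analysis step that tells them apart. This is more than a missing detail, because it bears on the primary comparison between ICUs.

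Bias needs two conditions: transfer shares that differ between hospitals, and settings that change over the first day or are carried over from the sending site. The documents show neither, so the size is unknown. The 1 to 9 FiO2 points are an illustration at the maximum delay and should not be read as an estimate. A reader might go further and conclude that the comparison of ventilation practice as a whole is invalid. The documents do not support that: the later readings are less affected, the group concerned is mainly transfers from non-participating hospitals, and the fields needed for most of the repair are already collected.

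**What to change.** 1. In Section 5.4.2, record ventilation time in the previous hospital in hours, so that it matches the 24-hour criterion in Section 4.3.
2. In Section 7, make the baseline between-hospital comparison in patients who were not transferred under ventilation. Alternatively, keep all patients and adjust for transfer status and, where intubation time is known, hours since intubation. Restriction needs no intubation times from other hospitals.
3. Report transferred patients' arrival readings separately.
4. State which reading the association models use, and handle baseline settings there in the same way.
5. Align the time origin in the Summary with Section 5.4.3.

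The change is one unit on the case report form and a few lines in Section 7. The cost is a smaller sample for the baseline comparison if it is restricted. If it is adjusted instead, some transferred patients will lack an intubation time, and retrieving times from non-participating hospitals takes effort.

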## 7. STATISTICAL ANALYSIS

Descriptive statistics will be used to describe the study population, and data are expressed in number and relative proportions for categorical variables and median (quartile 25% – quartile 75%) for continuous variables.

As the outcome of this study is urgently needed, data analysis will be done in two sequential steps. The first step includes an analysis of all patients admitted for invasive ventilation in one of the participating ICUs in the first four weeks after admission of the first COVID–19 patients, which was in all centers within the first weeks of March 2020. This part of the analysis focusses on ventilation practices in the first weeks of the pandemic in the Netherlands. This analysis may underestimate the effect of ventilation variables and parameters on outcomes, as many patients will not yet be weaned from the ventilator and remain admitted in the ICU. The second step includes an analysis of all COVID–19 patients admitted during the total 10 weeks PRoVENT COVID will enroll patients, with a complete follow up till day 90. This analysis will provide an answer to the question whether certain ventilator settings, variables and parameters are associated with patient–centered and other important outcomes.

All analyses will be performed using multilevel (patients nested in hospitals), mixed modelling with hospitals as random effect. Ventilatory variables and parameters will be compared among the groups, and absolute differences with the respective 95%–confidence interval (CI) will be calculated as the absolute difference from a mixed–effect linear model considering the hospitals as random effect to account for within–center clustering. Categorical variables will be compared as the risk difference from the same model.

Cumulative distribution plots will be used to demonstrate the cumulative distribution frequency of ventilation variables. Vertical dotted lines will represent the cut–off for each variable and the horizontal dotted lines the respective proportion of patients reaching each cut–off. Cut–offs to form matrices may use widely accepted values for each variable, specifically 8 mL/kg PBW for tidal volume, 10 cm H2O for PEEP, 30 cm H2O for plateau pressure, and 15 cm H2O for ΔP.

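### Two small data-window faults in 5.4.3: the paralytic item never covers 20:00 to 24:00, and the daily items run from an undefined admission

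*Combined protocol and SAP*

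**What the plan says.** Section 5.4.3 sets out several recording blocks.

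- **Ventilator, blood-gas and hemodynamic data** start "Within one hour after initiation of ventilation OR within first hour of arrival when the patient has been intubated in another hospital" and continue at 08:00, 16:00 and 20:00 over three days. The Summary (Methods) likewise runs the ventilator data from the start of ventilation.
- **Paralytic drugs** are a yes/no item at the same three clock times, each answer looking back 8 hours.
- **Daily items** (among them intubation status, SOFA, sedative and vasopressor doses, fluids, urine output and creatinine) are collected "Every day at 8:00 AM for 72-hour period after admission".

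Section 5.4.3 does not say which admission is meant. Section 5.4.2 is headed "Data on day of intubation OR admission to ICU if transferred from another hospital with mechanical ventilation". It lists hospital admission, "Date of ICU admission" and the date and time of intubation as separate items, and asks for the hours of non-invasive ventilation before intubation.

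**The concern.** The paralytic look-back would tile the day only if the recording times were 8 hours apart. They are 12, 8 and 4 hours apart, so part of each day is not asked about and part is asked about twice.

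The daily items raise a separate question. Section 5.4.3 starts two windows of the same length with different words. The plan itself allows admission and intubation to fall at different times. An abstractor who took hospital or ICU admission as the start would, in a non-transferred patient intubated later, collect some records from before ventilation and stop before the ventilator data stop. Sedative, vasopressor and fluid data would then describe different parts of the ventilation course in different patients. If the lag to intubation varied by hospital, hospitals could differ on these items through timing alone.

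**Working it through.** The plan states no figure for either point, so there is none to reproduce.

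**Paralytic item.** Inputs from 5.4.3: recording times 08:00, 16:00 and 20:00; look-back 8 hours.

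| Record | Hours covered now | Hours covered if asked since the previous record |
|---|---|---|
| 08:00 | 00:00–08:00 | 20:00–08:00 (12 h) |
| 16:00 | 08:00–16:00 | 08:00–16:00 (8 h) |
| 20:00 | 12:00–20:00 | 16:00–20:00 (4 h) |

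Now: 16 hours are covered once, 4 hours (12:00–16:00) twice, and 4 hours (20:00–24:00) not at all; 4/24 = 16.7%. Any use that touches 00:00–20:00 is caught by at least one record, so only use confined to the gap is missed. With the changed wording, 12 + 8 + 4 = 24 and each hour is covered exactly once.

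**Daily items.** Inputs: a 72-hour window (5.4.3), hence three 8 AM records; a 24-hour look-back for the fluid balance (5.4.3). The lag L from admission to intubation is not in the documents. The values below are assumptions that show the arithmetic, with the clock time of admission taken as uniform over 24 hours.

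The 8 AM records fall at U, U + 24 and U + 48 hours after admission, with U uniform on 0 to 24. Then, for L up to 48 hours:

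- overlap of the two windows = 72 − L hours;
- mean number of records on ventilated time = 3 − L/24;
- mean number of 24-hour balances wholly on ventilated time = 3 − (L + 24)/24 = 2 − L/24.

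| Assumed L (h) | Overlap (h) | Records on ventilated time, of 3 | Balances wholly ventilated, of 3 | Balances lost to the anchor alone |
|---|---|---|---|---|
| 0 | 72 | 3 | 2 | 0 |
| 12 | 60 | 2.5 | 1.5 | 0.5 |
| 24 | 48 | 2 | 1 | 1 |
| 48 | 24 | 1 | 0 | 2 |

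The row for L = 0 is the position after the anchors are matched. One balance of three still reaches back before ventilation. That loss comes from the look-back, not from the anchor.

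The gap can also run the other way, since 4.1 allows ventilation outside formal ICUs. If ICU admission is meant and comes M hours after ventilation starts, M/24 of the three 8 AM points in the first 72 ventilated hours are missed on average: 0.5 for M = 12 and 1 for M = 24.

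**The case against.** On the daily items, the strongest reply is that admission is shorthand for study entry. The 5.4.2 heading uses intubation, or ICU admission for patients transferred under ventilation. The baseline creatinine item in 5.4.2 pairs admission with intubation, and section 7 speaks of patients "admitted for invasive ventilation in one of the participating ICUs". On that reading the windows agree. This stands as a plausible reading, but none of these places defines the word in 5.4.3, and the 5.4.2 heading limits ICU admission to transferred patients, a limit that 5.4.3 drops.

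Four further points stand:

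- The lags are assumed, so the table does not show that data would be lost.
- Sedatives, vasopressors and fluid balances are endpoints only in the Summary; 5.1.2 does not list them and section 7 names no analysis of them.
- The study is retrospective and researchers visit the centers (sections 3 and 5.3). Missed days could be abstracted again while source records remain available, and the recorded intubation time and status would expose a mismatch.
- The reverse case is weak, because 4.1 may count another ventilation location as an ICU.

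On the paralytic item, the reply is that it is not named among the endpoints in the Summary, 5.1.1 or 5.1.2, and that the effect on an ever-used variable is probably small. Both are fair. They limit the size of the fault but do not remove it.

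**Conclusion.** Both points are minor. The paralytic gap is firm: it follows from the stated times and look-back alone, and leaves 4 of 24 hours unasked. The window mismatch is conditional on abstractors taking hospital or ICU admission, and it then affects only non-transferred patients whose ventilation does not start at that moment. Its size cannot be stated from the documents.

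A reader might infer that the daily data are in fact misaligned, or that the main results are at risk. The documents do not support either. Primary ventilator parameters have their own explicit anchor, and the baseline data of 5.4.2 do not use the 72-hour window. A reader might also infer that acute kidney injury is affected through the daily creatinine, but 5.4.3 collects it as its own yes/no follow-up item and nowhere derives it from those values. Whether prone positioning and recruitment maneuvers belong to the daily block cannot be told from the list layout, so nothing is claimed about them. Patients intubated at admission are unaffected, as are patients transferred under ventilation if admission means arrival.

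**What to change.** Make two wording changes in 5.4.3 and in the case report form.

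1. **Paralytics:** ask about use *since the previous time point*, with the first record looking back to the start of ventilation or to arrival. Keep the three recording times, because the ventilator data share them. The look-backs become 12, 8 and 4 hours, so summarise the item per day or as ever used, not by time point.
2. **Daily items:** replace *after admission* with the anchor already used for the ventilator data: *after the start of invasive ventilation, or after arrival if the patient was intubated elsewhere*.

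The second change aligns the two data windows and no more. Transferred patients would still enter at different points of their ventilation course, since 4.3 permits up to 24 hours of earlier ventilation in a non-participating hospital. The first 24-hour fluid balance can still include time before ventilation, and the analysis should say so.

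The cost is small: no extra patients, visits or procedures, and no change to the ventilator-data schedule. The one drawback is the unequal paralytic look-backs, which the per-day or ever-used summary handles.

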#### **2.1.2 Secondary objective**

To determine whether certain ventilation settings have an independent association with duration of ventilation.

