#### 5.1.2 Secondary study parameters

- Number of ventilation-free days and alive at day 28 (VFD-28);
- Duration of ventilation in survivors;
- Use of prone positioning;
- Use of recruitment maneuvers;
- Incidence of acute kidney injury (AKI);
- Duration of ICU stay;
- Duration of hospital stay;
- ICU mortality;
- Hospital mortality;
- 28-day mortality; and
- 90-day mortality.

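### After 72 hours the plan dates the end of ventilation only by extubation, so VFD-28 and duration of ventilation are undefined for tracheostomised and reintubated patients

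*Combined protocol and SAP*

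**What the plan says.** Duration of ventilation is the outcome of the secondary objective, which looks for an "independent association with duration of ventilation" (Section 2.1.2). Section 5.1.2 lists VFD-28 and "Duration of ventilation in survivors" among the secondary parameters, and Section 7 names VFD-28 as an outcome of the multivariable mixed models.

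The data behind these outcomes are set out in Sections 5.4.2 and 5.4.3:

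- **Start:** one date and time of intubation (Section 5.4.2).
- **First three days:** intubation status is recorded "Every day at 8:00 AM for 72-hour period after admission". Ventilation mode and settings are recorded "3 times a day at fixed time points (8:00 AM, and 4:00 PM and 8:00 PM) for a following 3-day period", after a first reading at the start.
- **Later follow-up:** the list opens with "Life status at day 7, day 28 and day 90" and goes on to "Alive (yes or no), and if not, the date of passing" and "Intubated (yes or no), and if not, extubation date", followed by the ICU and hospital discharge dates.

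No tracheostomy, restart of ventilation or last day of invasive support appears in these lists. Sections 5.1.2 and 7 name the two outcomes but give no rule for calculating either.

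**The concern.** Both outcomes need the date on which invasive ventilation ended. The listed item asks about the tube instead. The two come apart in two kinds of patient: those who go on being ventilated through a tracheostomy after the tube is removed, and those who are extubated and later reintubated. With neither the events nor a rule on file, the analyst cannot tell which date was entered or reliably reconstruct the right one.

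At stake are the outcome of the secondary objective and a modelled outcome. Section 7 itself expects many patients not to be weaned at the first analysis, so the plan anticipates long ventilation, where these events matter most. The primary objective, which describes ventilator settings, is not affected.

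**Working it through.** The plan has no figure to reproduce: there is no sample size calculation and no assumed VFD-28. The check sets the listed fields against what the outcomes need, then illustrates the size with assumed inputs.

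**Step 1. Which events the listed fields show**

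| Event | Shown by the listed fields? |
|---|---|
| Extubation or reintubation in the first 72 hours | Largely, through daily tube status and ventilation mode |
| Death while ventilated | Yes, through the date of death |
| Reintubated and still intubated at day 7, 28 or 90 | Yes as a status, but without a restart date |
| Reintubation beginning and ending between two of those days | No restart date; at most, two different extubation dates hint at it |
| Ventilation through a tracheostomy after 72 hours | No |

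**Step 2. One patient, several values**

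The dates are assumed. Day 0 is intubation and the patient is alive at day 28, so VFD-28 = 28 - day on which ventilation ends.

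*Tracheostomy on day 14, off the ventilator on day 24.*
- Tube removal taken as the end: 28 - 14 = 14 free days; duration 14 days.
- Last ventilation taken as the end: 28 - 24 = 4 free days; duration 24 days.
- Difference: 10 days on each outcome.

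*Extubated on day 6, reintubated on day 8, finally extubated on day 18.*
- First extubation: 28 - 6 = 22 free days; duration 6 days.
- Last extubation: 28 - 18 = 10 free days; duration 18 days.
- All free days counted: (8 - 6) + (28 - 18) = 12 free days; duration 18 - 2 = 16 days.
- Largest difference in VFD-28: 22 - 10 = 12 days.

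If the item is asked at each follow-up, this second patient could have day 6 entered at day 7 and day 18 at day 28. That supports 22 or 10, but not 12, because the restart on day 8 is not a listed field.

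**Step 3. Effect on the cohort mean**

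Overstatement of mean VFD-28 = share of patients affected x further ventilated days before day 28. Both inputs are assumptions. The share means patients who survive to day 28, are ventilated through a tracheostomy, and are all coded as extubated at tube removal.

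| Share | 4 days | 8 days | 12 days |
|---|---|---|---|
| 10% | 0.4 | 0.8 | 1.2 |
| 20% | 0.8 | 1.6 | 2.4 |
| 30% | 1.2 | 2.4 | 3.6 |

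With lower assumptions, 5-20% of patients affected and 2-10 days misassigned in one direction, the shift runs from 0.05 x 2 = 0.1 to 0.20 x 10 = 2.0 days.

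**The case against.** The strongest reply is that nothing in the documents shows a wrong value. The protocol never says that a patient ventilated through a tracheostomy is to be coded as not intubated. The item could be completed as presence and end of invasive ventilation, and a site could enter the last extubation. Researchers visit the centers to collect data (Section 5.3), which may make coding more uniform. The case report form is mentioned in Section 9.1 but is not part of the documents and may hold more detail. All of this stands, and it limits the claim to values that can be wrong or inconsistent. It does not supply the missing rule.

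A reader might infer more than the documents support:

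- *That extubation is the only information on when ventilation ended.* Early tube status, ventilation mode and date of death are also collected, and the extubation item is probably asked at all three follow-up days. The gap is confined to survivors after 72 hours.
- *That VFD-28 is necessarily overstated.* Coding a tracheostomised patient who is already off the ventilator as still intubated would understate it.
- *That hospital comparisons are biased because sites differ in tracheostomy timing.* No document describes timing by hospital, and the hospital random effect in Section 7 would absorb part of an average shift between hospitals. It would not correct an error that depends on a patient's own length of ventilation, but whether such an error distorts the associations is not shown.

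**Conclusion.** The concern holds in a limited form. For survivors after 72 hours, the listed data follow the tube rather than ventilation. They do not capture ventilation through a tracheostomy or reintubation between follow-up days, and the plan gives no derivation for the two outcomes that depend on this. The same patient can then receive VFD-28 values 10 to 12 days apart in the illustrations above.

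The effect on the cohort cannot be sized from the documents. The 0.4-3.6 days is a hypothetical upper bound: it assumes that every affected patient is miscoded in the same direction, and it leaves reintubation out. The gap merits correction because later analysis cannot reliably recover dates that were not collected.

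**What to change.** **Data collection (Section 5.4.3).** Keep the existing item to day 90 and add, also through day 90:
- the date of tracheostomy;
- the date of each restart and each stop of invasive ventilation, by tube or tracheostomy;
- the date of last invasive ventilation.

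The new dates should not stop at day 28. The second analysis step uses follow-up to day 90, and a day-28 limit would truncate duration in patients ventilated for longer.

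**Analysis (Section 7).** Count as ventilator-free only days without invasive ventilation by either route. Define the end of ventilation as the last stop of invasive ventilation by either route. State whether ventilator-free gaps are included in duration; in the reintubation example this is the difference between 18 and 16 days.

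**Cost.** A few extra date fields from charts that researchers already visit, plus a short paragraph in Section 7.
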